10.0 Reporting

10.1 Activities Required Prior to Initiation of the Study

10.1.1 Clinical Trial Agreement (CTA) and Financial Arrangements

A fully executed (signed by all required parties) CTA must be on file with the Sponsor prior to any investigator participating in this study. This agreement must explain the financial arrangement with the investigative site.

10.1.2 Institutional Review Board/ Research Ethics Board Protocol Approval

This study protocol must be submitted to and approved by the Investigator's Institutional Review Board (IRB) or Research Ethics Board (REB). A copy of the IRB or REB approval letter must be submitted to the Sponsor. The letter should identify the following:

- Protocol name and/or number.
- Date of IRB or REB meeting (if available).
- Date of approval.
- Date of expiration.
- Signature of IRB or REB.

10.1.3 ClinicalTrials.gov Registration

The Sponsor will be responsible for registering this study on www.ClinicalTrials.gov if required by local and national regulations.

10.2 Clinical Data Collection/Submission

10.2.1 Summary of Case Report Form Data Collection

Study data will be collected on source documents which may include study-specific worksheets provided by the Sponsor.

The following source document/CRF completion guidelines should be followed:

- Complete carefully and accurately.
- Complete header information consistently across all case report forms for each individual study subject (when study-specific CRFs are used).
- Be sure that data on the source documents match that which is entered through the electronic data capture (EDC) system.
- Use the study subject's unique Case ID number assigned as instructed. Do not provide information that is not requested on the CRFs.

- Ensure that all fields are completed. For fields completed by the subject, efforts should be made to obtain any missing responses prior to the subject completing their visit.

10.2.2 Data Submission

Completed CRFs will be submitted directly to the Sponsor by electronic data capture and submission via a method approved by the Sponsor. Every effort must be made to ensure data submission to the Sponsor is made within 30 days of the visit completion.

10.2.3 Quality Assurance of Data

The Investigator should ensure the accuracy, completeness, legibility, and timeliness of the data reported to the Sponsor in the CRFs and in all required reports. Data reported on the CRF, which are derived from source documents, should be consistent with the source documents or the discrepancies should be explained. All electronic systems used to create, modify, maintain, or transmit electronic study records will be validated. The Sponsor will maintain quality control systems, in accordance with the Sponsor's policies and procedures.

10.3 Investigator Reporting Responsibilities

The Investigator should ensure the accuracy, completeness, legibility, and timeliness of data reported to the Sponsor in accordance with this protocol. The Investigator or Designee will provide periodic reports to their IRB or REB as required to maintain IRB or REB approval throughout the study, and will provide any required final reporting to the IRB or REB upon study completion/termination. A copy of all IRB or REB re-approval letters must be submitted to the Sponsor. If the IRB or REB terminates or suspends its approval of the study, the Investigator or Designee will suspend study-related activities and will promptly notify the Sponsor. The Investigator should also promptly provide written reports to the Sponsor and the IRB or REB regarding any changes significantly affecting the conduct of the study, and/or increasing risk to the subjects.

10.4 Management of Intercurrent Events

10.4.1 Failure to Obtain Informed Consent

Study data will not be collected until the Informed Consent has been signed and dated by the candidate. If a candidate does not wish to participate (does not sign and date the Informed Consent), data for that candidate will not be collected for this study.

10.4.2 Surgical Reoperation or Revision

A reoperation of the index knee or revision of the SCP injection site may be performed at the discretion of the Investigator (e.g., due to progressive pain or disability, clinical or radiographic evidence of potential graft failure, etc.). A reoperation is defined as any surgical procedure on the index knee. For the

purposes of this protocol, a revision will be defined as any partial or total joint arthroplasty or any bone fixation, bone grafting or bone substitute procedure in the same compartment in the study knee.

The investigator is to dictate detailed operative notes that include the measures listed below, or have paper copies of the Surgical Reoperation Form completed during surgery to serve as a source document.

10.4.3 *Surgical Reoperation Documentation*

- Reason for Surgery
- Postoperative Diagnosis
- OR Time
- Anesthesia Type

All reoperations should be documented on an Adverse Event Form and the surgery documented on the Surgical Reoperation Form.

In the event that a revision occurs (defined as any partial or total joint arthroplasty or any bone fixation, bone grafting or bone substitute procedure in the same compartment in the index knee), the subject will be excluded from any future per protocol (PP) analysis of secondary endpoints, but should continue to be followed through the two-year endpoint for ITT analysis. An Adverse Event Form and Surgical Reoperation Form will be completed.

In the event that a reoperation occurs that does not involve revision of the BML site(s), an Adverse Event Form and Surgical Reoperation Form will be completed, and the subject will continue to be followed in the study per protocol. If possible, reoperations should not be performed within 6 weeks of the 12 and 24 month visits.

10.4.4 *Subject Cross-over Between Treatment Groups*

Subjects that display a lack of improvement in their baseline KOOS pain score by at least 10 points for at least two consecutive follow-up intervals, starting with the 3 and 6 month visits, or for any two consecutive visits thereafter, or subjects who show a trending decline in their KOOS pain score (as confirmed through an independent review of the case, see Section 10.4.5 below) may be considered for an additional procedure. The earliest a subject can be considered for an additional procedure is the 6 month follow-up visit. Subjects originally in the arthroscopy alone group may cross-over and be treated with Subchondroplasty with Arthroscopy, should they meet the aforementioned criteria, as determined by independent review. These subjects should not be unblinded until after the independent review's determination and will continue to be followed in the study per protocol through the 2 year endpoint.

10.4.5 *Independent Review of Worsening Cases and Potential Cross-over Treatment*

If any subject displays a lack of improvement or trending decline in their KOOS

pain scores as described in Section 10.4.4, the site shall submit documentation of the case to an independent, blinded review process for final determination of subject decline prior to unblinding the subject.

The independent review will be conducted by one or more physicians independent of the study and the clinical sites.

Information to be submitted to the independent review process will include all KOOS pain scores collected for the study and may include subject and knee history, pain medication and therapy use, as well as adverse event information, if applicable. Information submitted shall contain no indication of the treatment group to which the subject was assigned.

The independent review will result in a final documented assessment of subject decline irrespective of subject randomization. Once the assessment is received by the site, additional treatment options will be discussed with both groups of subjects prior to unblinding by the Investigator. If the subject was randomized to the Arthroscopy only group, they may proceed with the cross-over procedure in accordance with the protocol requirements and the assessment made during independent review.

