5.0 Introduction

5.1 Clinical Background

Subchondral bone defects, sometimes called bone marrow lesions (BMLs), are MRI-visible defects that can be seen on fat-suppressed MRI sequences (T2FS, PDFS, etc.) where they appear as a hazy white area against the background of darker bone. Pathologists have shown that BMLs represent a healing response to trauma such as micro trabecular fractures of the subchondral bone [1]. BML defects have been highly correlated with pain symptoms in the knee [2, 3]. However, BMLs and their impact on knee pain and function went relatively unrecognized in the orthopedic literature until 2011 [4].

Treatment options for BMLs have been limited in the past. For degenerative or chronic BMLs, treatments have included core decompression, extracorporeal shock wave therapy and pharmaceuticals [5]. While core decompression seeks to directly stimulate the bone through a surgical procedure, it does not fill the voids and defects in the bone and is not widely used to treat BMLs in the knee. Subchondroplasty® is a procedure first described in 2007 to fill subchondral osseous defects associated with bone marrow lesions using an injectable bone substitute material (BSM), AccuFill® [6]. AccuFill is an injectable, self-

setting, macro-porous, osteo-conductive, calcium phosphate bone graft substitute material that is intended for use to fill bony voids or gaps of the skeletal system of the extremities, spine (i.e. posterolateral spine), and the pelvis that are not intrinsic to the stability of the bony structure. These defects may be surgically created osseous defects or osseous defects created from traumatic injury to the bone. AccuFill is a bone graft substitute that resorbs and is replaced with new bone during the healing process. AccuFill has unique properties that allow it to flow through the osseous defects in trabecular bone and then set up hard at body temperature [7]. Two year results from a clinical study on 66 subjects considering TKA has shown improvements in subject reported pain and function with only 30% of subjects undergoing revision to TKA at 2 years [8]. The goal of this study is to evaluate the clinical outcomes associated with the on-label use of AccuFill during the Subchondroplasty procedure with arthroscopy compared to arthroscopy alone in subjects with bone marrow lesions in the knee.

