6.2 Primary Endpoint

The primary measure of clinical success is a composite clinical success (CCS) endpoint requiring:

- Freedom from secondary subsequent surgical intervention (SSSI); and
- Among subjects free from SSSI; an improvement in KOOS pain of at least 10 points.

For the purpose of this study, SSSI will include any partial or total joint arthroplasty or any bone grafting or bone substitute procedure in the study knee.

The 10 point threshold is consistent with ICRS recommendations for the use of changes in the KOOS pain score in responder endpoints [11].

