14.0 Statistical Considerations and Methodology

14.1 Primary Efficacy Endpoint Analysis

The primary measure of clinical success is a composite clinical success (CCS) endpoint requiring:

- Freedom from secondary subsequent surgical intervention (SSSI); and
- Among subjects free from SSSI; an improvement in KOOS pain of at least 10 points.

For the purpose of this study, SSSI will include any partial or total joint arthroplasty or any bone fixation, bone grafting or bone substitute procedure in the same compartment in the study knee.

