14.6 Analysis of Secondary Endpoints

The following secondary endpoints will be examined:

- 1) Comparison of mean change in KOOS Pain, ADL, Symptoms, Sports and Recreation, Quality of Life Subscale scores
- 2) Longitudinal comparison of KOOS subscales over 12 to 24 months post-surgery
- 3) Comparison of mean Numeric Pain, EQ-5D and Global Satisfaction scores, where available
- 4) X-ray evaluation of joint space narrowing, osteophyte and cyst formation and subchondral sclerosis, where available
- 5) MRI analysis of bone marrow lesion variables, where available
- 6) Incidence and time to resolution of post-operative complications and adverse events
- 7) Incidence and time to joint injections, where available
- 8) Incidence and time to re-operations and revisions
- 9) Number of visits to healthcare providers, diagnostic or treatment procedures, and support devices; use of pain medication; and days of productivity lost, where available.

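### Protocol cross-over counts as a CCS failure and a revision but is offered only to arthroscopy-alone subjects, so both comparisons partly measure access to cross-over

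*Combined protocol and SAP*

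**What the plan says.** Section 6.2 defines the surgical component of CCS: "SSSI will include any partial or total joint arthroplasty or any bone grafting or bone substitute procedure in the study knee". Section 14.1 words it differently, adding fixation and a compartment limit: "SSSI will include any partial or total joint arthroplasty or any bone fixation, bone grafting or bone substitute procedure in the same compartment". Neither exempts the protocol cross-over. Section 5.1 describes Subchondroplasty as a procedure to "fill subchondral osseous defects associated with bone marrow lesions using an injectable bone substitute material (BSM), AccuFill". Sections 7.0 and 10.4.2 define a revision in nearly the same terms as the SSSI of 14.1.

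Under Section 10.4.4, a subject in either arm may be considered for an additional procedure. The trigger is a KOOS pain gain below 10 points at two consecutive visits (starting with months 3 and 6), or a trending decline. The earliest time is the month-6 visit. Independent blinded review must confirm the case, after which "additional treatment options will be discussed with both groups of subjects prior to unblinding by the Investigator" (10.4.5). The named cross-over is for one arm only. Section 10.4.4 says "Subjects originally in the arthroscopy alone group may cross-over and be treated with Subchondroplasty with Arthroscopy, should they meet the aforementioned criteria", and Section 10.4.5 repeats it: "If the subject was randomized to the Arthroscopy only group, they may proceed with the cross-over procedure".

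Section 14.2 tests CCS one-sided at 0.01 at month 12 and, failing that, at 0.04 at month 24. Section 14.6 item 8 lists "Incidence and time to re-operations and revisions". Section 14 has no rule for cross-over, and Section 14.9 deals only with subjects who cannot be evaluated for CCS.

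**The concern.** The 10-point cut that defines success in CCS also opens the way to cross-over. Take two subjects, one per arm, with the same poor scores at months 3 and 6 and the same later recovery. If the control takes the cross-over, CCS records a failure at months 12 and 24 whatever the later score. The S+A subject, if no SSSI follows, is scored on pain at the visit and can be a success.

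The difference in CCS then contains a part that reflects which arm was offered a particular operation. The revision comparison contains it more directly, since every cross-over adds a revision in the control arm. Both shifts favour S+A. Nothing in the plan would let a reader separate this part from a treatment effect.

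**Working it through.** **1. The plan's own figure.** Inputs from 14.2 and 14.5: CCS 0.80 and 0.60, ratio 2:1, 80% power; one-sided 0.04 is the level that reproduces the total. Pooled rate = (2 x 0.80 + 0.60)/3 = 0.733. Controls needed = [1.751 x sqrt(1.5 x 0.733 x 0.267) + 0.842 x sqrt(0.16/2 + 0.24)]^2 / 0.20^2 = 50.7. With continuity correction: (50.7/4) x [1 + sqrt(1 + 6/(50.7 x 2 x 0.20))]^2 = 58.0. This gives 58 + 116 = 174, as stated, so the checks below use 116/58.

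**2. Who is misclassified.** Only a control who crosses over and would otherwise have been a success. Cross-overs who would have failed anyway add no bias. Let q be the share of all controls converted in this way, net of any similar loss in S+A. With true success rate p in both arms, observed control CCS is p - q.

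**3. Effect of q at month 24.** Exact binomial probability that the pooled one-sided z test at 0.04 rejects, 116/58:

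| q | controls of 58 | p = 0.60 | p = 0.70 | p = 0.80 |
|---|---|---|---|---|
| 0 | 0 | 0.041 | 0.042 | 0.042 |
| 2% | about 1 | 0.068 | 0.072 | 0.078 |
| 5% | about 3 | 0.131 | 0.144 | 0.164 |
| 10% | about 6 | 0.306 | 0.337 | 0.390 |

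To relate q to its parts: q = (early non-responders) x (uptake) x (late improvement). Assuming 40%, 25% and 10%, q = 0.40 x 0.25 x 0.10 = 1%, p = 0.60 + 0.40 x 0.10 = 0.64, and the probability is 0.055. Assuming 40%, 50% and 20%, q = 4%, p = 0.68, and it is 0.114.

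**4. The whole 0.01/0.04 sequence.** Simulation with the same KOOS pain course in both arms. Change at months 3, 6, 9, 12, 18 and 24 = mean + subject effect + visit noise; total SD 20; within-subject correlation (ICC) 0.5 to 0.85; mean set so that 60% or 70% reach 10 points. Controls below 10 points at two consecutive visits cross over with the stated probability and then count as failures. SD, ICC and uptake are assumptions.

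| uptake among eligible controls | chance of declaring superiority |
|---|---|
| none | about 0.05 |
| 10% | 0.05-0.08 |
| 25% | 0.07-0.12 |
| 50% | 0.11-0.25 |

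The upper ends come from ICC 0.5. At ICC 0.85 and 25% uptake the result is 0.07-0.08. At ICC 0.5-0.7, control CCS at month 24 falls by about 2.5-4 points at 25% uptake and 5-8 points at 50%.

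**5. Two variations.** If control uptake is 50% and S+A subjects have SSSIs at half that rate, the chance is 0.07-0.12. If the two-visit KOOS rule is applied from the data to both arms alike, it returns to about 0.04-0.05, and CCS falls by about 6-16 points in each arm.

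**The case against.** Four points on the other side have weight.

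- A reader might infer that the overall 0.05 error rate is broken. The documents do not support that wording. The null hypothesis in 14.2 is stated on CCS itself, and CCS includes SSSI. If cross-over lowers control CCS, that null is false, and rejecting it is not a type I error of the planned test. What is affected is the meaning of a rejection, not the alpha split.
- A reader might infer that S+A subjects have no corresponding way to fail. They have other ways. Sections 10.4.4 and 10.4.5 open additional treatment to both arms, and 10.4.2 allows revision of the injection site. Arthroplasty, grafting or fixation in S+A is also an SSSI. Equal net losses among would-be successes would remove the bias. The documents give no reason to expect equality, because one named procedure belongs to one arm.
- Cross-over is not a low hurdle. It needs repeated non-response or decline, blinded confirmation and the subject's choice of more surgery, so uptake may be small. The model also has no time trend, so some of its late improvers are noise around the threshold. The review makes the finding of decline fair between arms; it does not alter which arm may then cross over.
- Enrollment stopped early because control success was unexpectedly high (Section 7.0). That means fewer eligible cross-overs and a smaller prospect of superiority, and final numbers are not given. It does not remove the month-24 test, the month-24 follow-up or the revision endpoint.

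Section 10.4.6 mentions being revised and having the cross-over procedure separately. This may hint that cross-over was not meant to be an SSSI, but no text says so. On that reading, controls would be scored on pain after receiving Subchondroplasty, which also needs a stated rule.

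**Conclusion.** The concern stands as a matter of interpretation. Followed exactly, the plan scores a crossed-over control as a CCS failure and a revision, and offers that procedure to one arm only. The CCS and revision comparisons therefore combine treatment effect with availability of cross-over, in the direction of S+A.

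The amount is conditional. It is nil with no net conversion, and material if more than a few of the 58 planned controls are converted (about 3 give 0.131-0.164 at month 24 against a nominal 0.04). The 116/58 figures are for the planned size. It would go too far to say that the design is likely to yield a false superiority claim: uptake is not in the documents, and the early stop points the other way. This should be fixed before the month-24 analysis, but it does not invalidate the primary test.

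**What to change.** No treatment rule changes, and the primary endpoint is not redefined after the interim look.

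1. Keep CCS as primary. State in 14.1 that a protocol cross-over counts as an SSSI, and reconcile the definitions in 6.2 and 14.1.
2. Before the month-24 analysis, pre-specify two sensitivity analyses:
   - (a) A symmetric CCS that applies the 10.4.4 two-consecutive-visit KOOS criterion from the data, identically in both arms, whether or not a procedure followed. State how controls who crossed over on a trending decline alone are handled.
   - (b) An analysis in which cross-over alone is not failure, and month-12 or month-24 status after it is imputed from KOOS scores before cross-over.
3. Describe any superiority finding as robust only if (a) and (b) agree with the primary result.
4. In 14.6 item 8, report cross-overs separately from other SSSIs and revisions.

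The cost is SAP wording and one or two extra analyses on data already collected. The drawback of (a) is a CCS rate lower by about 6-16 points in both arms, so it should be read as a between-arm comparison and not as a success rate.

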9.7.2 Telephone Interviews

The Study Coordinator will schedule a call with the subject within the visit window. During the call, the subject is to be queried regarding the occurrence of any Adverse Events and Serious Adverse Events, per Section 11.0 Safety Management—Medical Events/Adverse Events. Any adverse event that results in reoperation or revision is to be recorded as a Serious Adverse Event.

The subject is to be queried regarding any reoperations of the index knee. All reoperations are to be documented using the Surgical Reoperation Form, per Section 10.4.2.

If the subject has not already completed the applicable PROs, these subject reported outcome surveys may be completed during the telephone interview. The Study Coordinator is to read each question and record the answer given.

The Study Coordinator is to document the phone interview, including any completion of outcome measures over the phone, in the subjects' study files.

Table 1. Schedule of Events

	Visit 1	Visit 2	Visit 3	Visit 4	Visit 5	Visit 6	Visit 7	Visit 8	Visit 9
Procedures	Study Admit/ Pre-operative	Operative	6 Weeks	3 Months	6 Months	9 Months	12 Months	18 Months	24 Months
Visit Window	≤60 days Prior to Surgery		±10 Days	±30 Days	±30 Days	±30 Days	±2 Mos	±2 Mos	±2 Mos
Informed Consent ¹	X								
Inclusion & Exclusion Criteria	X								
Demographic Form	X								
Knee Examination	X								
Knee History	X								
Medical History	X								
Pain Medications	X								
X-Ray Series	X								
MRI ¹	X								
Telephone Follow-Up			X	X	X	X	X	X	X
Screen for Adverse Events ²		X	X	X	X	X	X	X	X
KOOS Knee Survey	P		P	P	P	P ³	P	P	P
Numeric Pain Scale	P		P	P	P		P	P	P
EQ-5D	P								
Healthcare Utilization	P								
Return to Work									
Surgical Documentation		X							
Serious Adverse Event ²		(X)	(X)	(X)	(X)	(X)	(X)	(X)	(X)
Protocol Deviation ²		(X)	(X)	(X)	(X)	(X)	(X)	(X)	(X)
Surgical Reoperation ⁴			(X)	(X)	(X)	(X)	(X)	(X)	(X)
Study Exit ⁵		(X)	(X)	(X)	(X)	(X)	(X)	(X)	(X)

X Investigator completed forms

P Subject completed forms

¹Informed Consent and Baseline MRI to be done within 90 days of study enrollment.

² Case Report Forms to be completed if/when event occurs.

³ KOOS Pain Subscale *only* at 9 month visit

⁴ Surgical Reoperation form will be completed if the investigator performs any procedure on the index knee regardless of whether the subject's change in condition is related to the initial study procedure.

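### By-group safety and revision tables do not separate the cross-over Subchondroplasty offered to controls from the outcomes of arthroscopy alone

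*Combined protocol and SAP*

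**What the plan says.** Section 10.4.4 allows an additional procedure for subjects whose KOOS pain has not improved by 10 points at two consecutive visits, or is trending down. On timing: "The earliest a subject can be considered for an additional procedure is the 6 month follow-up visit". It names one such procedure, for one arm: "Subjects originally in the arthroscopy alone group may cross-over and be treated with Subchondroplasty with Arthroscopy". These subjects stay in follow-up to 2 years. Section 10.4.5 adds that, after the blinded review, "additional treatment options will be discussed with both groups of subjects prior to unblinding by the Investigator".

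The classification rules in 10.4.2 and 10.4.3 are:

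- Reoperation: "A reoperation is defined as any surgical procedure on the index knee".
- Revision: arthroplasty, or "any bone fixation, bone grafting or bone substitute procedure in the same compartment in the study knee".
- Recording: "All reoperations should be documented on an Adverse Event Form". Footnote 4 to Table 1 agrees: "Surgical Reoperation form will be completed if the investigator performs any procedure on the index knee".

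Section 9.7.2 adds: "Any adverse event that results in reoperation or revision is to be recorded as a Serious Adverse Event".

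On reporting, the synopsis tabulates events by group from surgery to the end of the study. Section 14.7 gives counts and percentages per subject, event counts by visit interval, incidence by treatment group, and listings with onset and relatedness. Section 14.8 uses the mITT population for safety. Secondary endpoint 8 (6.3 and 14.6) is the incidence of, and time to, re-operations and revisions.

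**The concern.** Neither definition in 10.4.2 exempts the cross-over operation, and nothing in 14.6 to 14.8 labels it, stops control follow-up at it or splits the control column there. A control who receives the study device is therefore counted in the arthroscopy-alone column as a reoperation and a revision. Any later AccuFill event in that subject is counted there too.

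This matters because 7.0 says follow-up continues after the early stop in order to monitor revisions, reoperations and adverse events, alongside KOOS and pain scores. These tables are a main remaining output. A reader will want to know how often arthroscopy without the device leads to further surgery or serious events, and the planned rates do not answer that. The point is confined to the safety tables and secondary endpoint 8; the composite primary endpoint is not at issue.

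**Working it through.** **Does the operation fall under each rule?**

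- *Reoperation:* yes. It is surgery on the index knee.
- *Revision:* yes. It places a bone substitute at the study lesion, and inclusion criterion 7 puts study lesions in one compartment.
- *Adverse Event Form:* yes. 10.4.3 covers every reoperation. 10.4.6 recognises the cross-over procedure, but only to waive a deviation form.
- *SAE:* possible, not settled. 9.7.2 makes serious the adverse event that leads to reoperation. But 11.0 says a pre-existing event is not an adverse event unless its severity or intensity changed. A subject who crosses over for lack of improvement may have unchanged baseline pain, so sites may differ. The carve-out in 11.1 for procedures the protocol requires does not clearly apply, because cross-over is only permitted.

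**Size.** The plan states no cross-over count, no reoperation, revision or SAE rate, and no actual arm sizes after the early stop. There is no figure of its own to reproduce, and what follows is illustration.

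Assumed inputs:

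- Cross-over share c = trigger × take-up: 0.20 × 0.25 = 5%; 0.40 × 0.25 = 10%; 0.40 × 0.50 = 20%. The 0.40 is 1 − 0.60, from the AA success rate in 14.5. The 20% end is probably high, since 7.0 reports unexpectedly high AA success.
- r = additional procedures in S+A relative to cross-over in AA.
- Revisions from other causes: p = 10% in both arms.
- SAEs from other causes: 5% AA and 10% S+A (true ratio 2.0).
- s = share of additional procedures recorded with an SAE.

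*Revision gap, AA minus S+A, in percentage points.* Independence: (1 − p) × c × (1 − r). Full overlap: max(p, c) − max(p, rc).

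| Case | c = 5% | c = 10% | c = 20% |
|---|---|---|---|
| Independent, r = 0 | 4.5 | 9 | 18 |
| Independent, r = 0.5 | 2.25 | 4.5 | 9 |
| Independent, r = 1 | 0 | 0 | 0 |
| Full overlap, r = 0 | 0 | 0 | 10 |
| Full overlap, r = 1 | 0 | 0 | 0 |

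Under independence the gap turns negative if r exceeds 1.

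*SAE ratio, S+A over AA (independence, s = 1).* AA = 0.05 + 0.95c; S+A = 0.10 + 0.90rc.

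| | c = 5% | c = 10% | c = 20% |
|---|---|---|---|
| AA recorded | 0.0975 | 0.145 | 0.24 |
| S+A, r = 0.5 | 0.1225 | 0.145 | 0.19 |
| Ratio, r = 0.5 | 1.26 | 1.00 | 0.79 |
| S+A, r = 1 | 0.145 | 0.19 | 0.28 |
| Ratio, r = 1 | 1.49 | 1.31 | 1.17 |

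Here s and c act only through their product, so halving s has the same effect as halving c; at s = 0 the ratio stays at 2.0. At r = 1 the fall in the ratio is mostly dilution: the S+A minus AA difference is 4.75, 4.5 and 4 points against a true 5.

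*Later AccuFill events.* Cross-over cannot precede month 6, so the device-exposed share of control follow-up is at most c × 18/24 = 3.75%, 7.5% or 15%. An assumed 5% event incidence among those crossing over adds 0.05 × c = 0.25, 0.5 or 1.0 points to the control column. This is the smaller part.

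**The case against.** The strongest reply is that the as-randomised table is right. Surgery in a control after confirmed decline is a real outcome of being assigned to arthroscopy alone. That stands. A reader might infer that a control-arm excess would be spurious, or a bias toward the device. The documents do not support this: as a comparison of strategies the excess is genuine. What fails is only its reading as a rate for arthroscopy without the device.

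Second, S+A subjects may also have additional procedures, and the same definitions and SAE rule apply to them. That also stands. A reader might set S+A procedures to zero and find the assumed SAE ratio of 2.0 cut to 1.03, 0.69 or 0.42 (0.10 over the AA rates above). Section 10.4.5, which has options discussed with both groups, gives no basis for zero. Equal take-up cannot be presumed either, because only controls have a named device procedure.

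Third, the 14.7 listings and interval counts allow tracing. A control can have an AccuFill-related event only after receiving AccuFill, so such events identify themselves. True, but this yields no separate rate or denominator and leaves the cross-over operation in the control reoperation and revision counts.

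Fourth, 10.4.3 drops revised subjects from later per-protocol analysis of secondary endpoints. But 14.8 names that population only for the primary variables and uses mITT for safety.

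Finally, the safety tables are descriptive, with no hypothesis test. That limits the stakes.

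**Conclusion.** The point holds as a gap in reporting. As written, the plan puts the cross-over procedure and device-exposed follow-up time into the arthroscopy-alone rates without a label. This assumes that group means randomised group; the plan does not say so, but it is the natural reading.

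The size and direction of the net effect cannot be fixed from the documents. They depend on take-up, on overlap with revisions that would have happened anyway, and on additional procedures in S+A. In the cases worked, the revision gap runs from 0 to 18 points. The upper end needs 20% cross-over, independence and no S+A revision-type procedures together. Overlap is plausible, because declining knees are the ones likely to be revised.

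A reader might also infer that every cross-over becomes an SAE, or that the SAE comparison reverses. The first is not established, given 11.0. The second appears at half S+A take-up only when cross-over is above 10% (at 10% the ratio is 1.00), and not at all at equal take-up, with every additional procedure recorded as an SAE.

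**What to change.** In 14.7, and for secondary endpoint 8, keep the as-randomised table as the main one and say that it is as randomised. Add supportive tables with:

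1. control events and person-time up to the date of cross-over surgery;
2. a separate 'AA then SCP' column, with its own denominator and person-time, for events on or after that date;
3. cross-over Subchondroplasty as its own row, beside a row for additional procedures in S+A, with reoperation, revision and SAE incidence shown with and without these procedures in both arms.

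No new visits or data are needed. Adverse event onset dates are collected under 11.2, the Surgical Reoperation Form identifies the operation, and time to re-operation already requires its date. The cost is a paragraph of text and some table programming, including person-time, which 14.7 does not now use. One downside is statistical: stopping control time at cross-over removes subjects who are doing badly, so that censoring is informative. The split tables should be labelled supportive and read beside the main table.
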